Description of location(s) where consent will be obtained:

George E Wahlen Department of Veterans Affairs Hospital, Salt Lake City Health Care System.

Description of the consent process(es), including the timing of consent:

Consent process is now part of the IRB study # 00082763. No separate consent process will be used.

Requested Waivers/Alterations of Consent:

Waiver of Informed Consent VA Waiver of Consent for Recruitment Purposes Only

Procedures:

-Patient selection

All patients selected to participate in the "Safety Study of Percutaneous Osseointegrated Implants for Prosthetic Attachment (IRB #00082763)" will participate in this study. As this is safety evaluation study, subjects will not be randomized. Follow-up end point will be 1 year post 2nd stage surgery.

Patients will be consented through IRB study # 00082763.

- Obtaining consent

Patients are consented as part of the IRB #00082763 consenting process

- Sample collection

Samples (skin swabs, tissue and blood) for this study will come from the samples collected and tissue-banked as part of the IRB # 00082763.

Collection process is described in IRB # 00082763. Briefly, samples will be collected from each patients at different pre- and post-operative time points (see below).

Pre-op stage 1/day of the procedure, 3+/-7 days of stage 1 post-op, pre-op of stage 2/day of procedure, day 7 +/- 7 days of stage 2, 2 wk +/- 14 days of Stage 2, and 6wk +/- 14 days, 3, 6,9, 12 mo +/- 30 Days of stage 2.

-Analysis

-Reporting

Procedures performed for research purposes only:

Statistical Methods, Data Analysis and Interpretation

Statistical analysis: A sample size of n=10 patients is planned to be used.

Sample Size Justification. A sample size of n=10 patients will be used. Even if the specific comparisons, which involve a single predictor variable, described for Aims 1 to 3 reveal trends that are not statistically significant, it would be sufficient to show that overall model fit is significant. That is, a significant multivariable curvilinear correlation with pro-inflammatory cytokines, for example, would demonstrate that Bio-Plex array is potentially a sensitive indicator of inflammation and/or infection, provided that a visible shift in the graphed growth curve occurs

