In this microbiota study, the temporal dynamics of the stomal bacterial ecology of these ten patients were investigated over the duration of one-year following the second surgery. skin swab samples were collected at regular intervals using swabs obtained from 3 different sites. Pre-surgery data was used as a baseline, thus, each patient had their internal control, and the microbiota changes to the individual patient's pre- and post- skin swab samples were compared. The DNA extraction were performed using the standard procedure. The 16S ribosomal RNA genes were amplified using broad range PCR primers targeted to the V1-V3 hypervariable region (V1V3 Forward primer 5'-AGAGTTTGATCCTGGCTCAG-3' and V1V3 Reverse primer 5-ATTACCGCGGCTGCTGG-3'), with barcodes unique to each sample. PCR reactions were carried out in quadruplicate using high fidelity Accuprime Taq. The resulting 16S rDNA amplicons were purified using a 1:1 volume of SPRI beads, quantified using PicoGreen, pooled in equal amounts, and sequenced on the Illumina MiSeq using 2x300 bp chemistry. Extraction blanks and DNA-free water were subjected to the same amplification and purification procedure to allow for empirical assessment of environmental and reagent contamination. Sequencing was performed by the PennCHOP Microbiome Center on the Illumina MiSeq instrument. Sequencing results were then processed using the hmmUFOtu workflow. Reads were demultiplexed using the prior mentioned barcodes. Individual reads (with $\geq 97\%$ identity) were treated as same species sequences, and were clustered and assigned to operational taxonomic units (OTUs) using the Greengenes 13_8 database. OTUs that were found to represent just one sequence in one sample were also removed. Any reads assigned to Cyanobacteria, a common contaminant, were also removed. OTU tables and phylogenetic trees output from hmmUFOtu were then further analyzed using the phyloseq package in R. This analysis included rarefaction of samples down to an even depth of ~ 1000 sequences per sample. Alpha and beta diversity metrics were computed using the vegan package.

All statistical analysis was performed in R. For testing statistically significant differences between populations, the nonparametric Wilcoxon rank-sum test was used (wilcox.test function in R). Due to the sample losses from rarefaction, the

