unpaired test was used. Multiple testing correction was also applied with the `p.adjust` function, using the false discovery rate correction. For differential abundance testing, the DESeq2 and phyloseq packages were used with default settings. Sample similarity was calculated using the Weighted UniFrac, Unweighted UniFrac, and Bray Curtis Beta diversity metrics, and/or statistical comparisons of community composition. The Adonis function (PERMANOVA test), from the vegan package was applied to each of the aforementioned metrics. Dirichlet multinomial mixture modelling was performed using the DirichletMultinomial package. Ordination was performed using the labdsv package.

Whole Blood RNA expression data

Whole-blood samples were collected from these patients at the following time points: pre-surgery 1 (PrS1), post-surgery 1 (PoS1), pre-surgery 2 (PrS2), post-surgery 2 week 1 (PoS2-W1), post-surgery 2 week 2 (PoS2-W2), post-surgery 2 month 1 (PoS2-M1), post-surgery 2 month 3 (PoS2-M3), post-surgery 2 month 6 (PoS2-M6), post-surgery 2 month 9 (PoS2-M9), and post-surgery 2 month 12 (PoS2-M12). Whole-blood RNAs were isolated and undergone complete RNA sequencing, where single-end base pair sequencing was performed at the University of Utah Core genomic facility. Gene read counts were quantified via featureCounts and differential gene expression (DEG) analysis was performed using DESeq2.

For the DEG analysis, pair-wise comparisons were made in two sets: first, between PrS1 and all subsequent time points, second between PrS2 and all subsequent time points. Results from the DEG analysis were used to perform an enrichment analysis, which implemented topGO's elim graph algorithm paired with the Kolmogorov-Smirnov test for significance. Enrichment analysis was run on each of the Gene Ontology's (GO) sub ontologies: biological process (bp), cellular component (cc) and molecular function (mf).

References:

1. Bland, J.M. and D.G. Altman, Calculating correlation coefficients with repeated observations: Part 1--Correlation within subjects. *BMJ*, 1995. 310(6977): p. 446.
2. Bland, J.M. and D.G. Altman, Calculating correlation coefficients with repeated observations: Part 2--Correlation between subjects. *BMJ*, 1995. 310(6980): p. 633.

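### No repetition, averaging or seed is stated for rarefaction to about 1000 reads, so diversity verdicts near the threshold can depend on the draw; averaging over draws costs only computing time.

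*Combined protocol and SAP*

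**What the plan says.** All the relevant text is in the Microbiota analysis section of the combined protocol and SAP. The OTU tables "were then further analyzed using the phyloseq package in R", and then: "This analysis included rarefaction of samples down to an even depth of ~ 1000 sequences per sample". The next sentence is "Alpha and beta diversity metrics were computed using the vegan package".

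Groups are compared by the Wilcoxon rank-sum test. The reason given for not pairing begins "Due to the sample losses from rarefaction, the" and ends "unpaired test was used". P-values are adjusted "using the false discovery rate correction". Adonis (PERMANOVA) is applied to three dissimilarities: Bray-Curtis and the weighted and unweighted forms of UniFrac. Ordination follows.

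The section does not give the number of rarefaction draws, the random seed, any averaging over draws, or any check of sensitivity to the draw. It does not name the alpha metrics or report reads per swab before rarefaction. On size, the Sample Size Justification says "A sample size of n=10 patients will be used".

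**The concern.** Rarefaction replaces a swab's full read count with a random subsample. If it is done once, each retained swab carries sampling noise that comes from the random number generator and not from the patient or the sequencer. The point concerns the swabs that are kept; the swabs that fall below the depth are a separate matter.

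The noise falls mainly on measures that count presence. A rare organism is either in the draw or not, and that changes observed richness and unweighted UniFrac. Abundance-weighted measures give such organisms little weight.

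With ten patients and an unpaired rank-sum test, p-values near the threshold are plausible. For those, whether a diversity change is called significant can depend on which subsample was taken. Aim 1 is to characterise the microbiota, so these metrics are central to it, and the noise can be removed without new data.

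**Working it through.** **The plan's own figure.** The plan gives no figure on this point apart from the depth. Its one computed design figure (r = 0.71 with n = 10) concerns a correlation and has no bearing on rarefaction.

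**Inputs from the documents.** Depth of about 1000 reads; 10 patients; unpaired rank-sum; three dissimilarities tested by Adonis; false discovery rate correction; some swabs lost to rarefaction, number not stated.

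**Inputs assumed.** Reads per swab, number of OTUs, community shape, effect size, and 10 v 10 swabs (that is, no loss).

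**Step 1: the mechanism.** Take a taxon that makes up 0.1% of a swab's reads. The probability that a 1,000-read draw misses it is:
- with replacement: 0.999^1000 = 0.368;
- without replacement, 20 of 20,000 reads: the product of (19000 - i)/(20000 - i) for i = 0 to 19, which is 0.358;
- without replacement, 3 of 3,000 reads: (2000 × 1999 × 1998)/(3000 × 2999 × 2998) = 0.296;
- without replacement, 1 of 1,000 reads: 0.

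In the 20,000-read swab a single draw scores this taxon 1 (probability 0.642) or 0 (probability 0.358), a draw variance of 0.642 × 0.358 = 0.230. The closed-form expected richness, the sum over taxa of 1 - C(N - N_i, 1000)/C(N, 1000), scores it 0.642 every time. The variance goes. The shortfall from 1 stays, because it comes from the depth. As a library approaches 1,000 reads, the draw noise vanishes.

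**Step 2: how often the verdict changes.** If a fraction f of draws gives p < 0.05, two independent draws disagree with probability 2f(1 - f). Five simulation set-ups, all 10 v 10 and unadjusted p, gave these disagreement rates:

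| Set-up (OTUs; reads per kept swab) | Richness | Shannon or Bray-Curtis | Presence/absence PERMANOVA |
|---|---|---|---|
| A: 200; 20,000 (1,500 contrasts per setting) | 5% null, 13-15% with an effect | not run | not run |
| B: 300; 1,000-3,000, 3,000-30,000 or 20,000-100,000 (80 datasets per setting, 60 draws each) | 1.4-10.2% | Shannon 0.3-3.7% | not run |
| C: 200; 3,000-40,000 (200 datasets per setting, 999 permutations) | 4.5-17.5% | Bray-Curtis 0-4% | 6-6.5% null, 15.5-19% intermediate effect |
| D: 200; 20,000, or 1,000-1,500 (800 contrasts per setting, about 40% power) | 23.5%, 14% | Shannon 8%, 4% | not run |
| E: 200; 1,000-3,000 or 3,000-40,000 (199 permutations) | 3-15% | Bray-Curtis 1-3% | 6-19% |

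In C, at large effects almost no beta-diversity verdict changed (0-1.5%). Part of the PERMANOVA disagreement is permutation error: at p = 0.05 its standard error is √(0.05 × 0.95/199) = 0.015 with 199 permutations and √(0.05 × 0.95/999) = 0.007 with 999. Presence/absence dissimilarity (Jaccard in C) stood in for unweighted UniFrac because no tree was simulated. Weighted UniFrac was not simulated.

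**Step 3: where the changes fall.** In B, significance for richness changed at least once over 60 draws in 7.5-42.5% of datasets, so at least 57.5% gave the same verdict under every draw. Where the draw-averaged p lay between 0.02 and 0.10, 75-100% (richness) and 33-67% (Shannon) gave both verdicts, on only 6-28 datasets per setting.

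**Step 4: share of variance.** In B, for richness at 3,000-30,000 reads with an effect, draw SD was 4.321 and between-swab SD 32.169, so the share is 4.321²/(4.321² + 32.169²) = 18.7/1,053.5 = 1.8%. Over all B settings and both metrics it was 0.15-2.4%. It was about 10% in A, 29-48% in C, and in D 7% (1,000-1,500 reads) or 26-28% (20,000 reads). The denominators are not identical, but the spread shows how much depends on the assumed community.

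**Step 5: power from averaging.** B: none (0.50 v 0.50 for richness, 0.29 v 0.28 for Shannon). A: about 2 points for richness. E: about 3-6 points for richness. Presence/absence PERMANOVA: C, 0.725 to 0.82 and 0.81 to 0.935 (9.5 and 12.5 points); E, about 0.78 to 0.88-0.91 (10-13 points).

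**The case against.** The strongest reply is that the section is silent rather than wrong. A reader might infer that the plan states a single draw. It does not: the function, seed and number of draws are simply absent. That stands, and one draw must be presented as the natural reading only. If several draws were made, how they were combined is also unstated.

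A reader might also infer that the diversity results cannot be reproduced from the same sequences. That goes too far, since a recorded seed makes a single draw exactly repeatable. What remains is dependence on an arbitrary choice, mainly near the threshold.

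Third, the percentages are not stable. The documents do not say that observed richness was used, and two of the three named dissimilarities are abundance-weighted. A uniform 20,000 reads sits poorly with the acknowledged sample losses, which imply that depth varies and that some swabs fall below the cut. Kept libraries close to 1,000 reads carry little draw noise. The simulations count changes at unadjusted p < 0.05, while the plan adjusts and states no alpha for the microbiota tests. All of this stands; it is why only a range is given.

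Fourth, it is tempting to read the roughly 37% chance of missing a 0.1% taxon as the harm that averaging would cure. Much of that belongs to the depth, which averaging leaves as it is.

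Finally, this is a ten-patient feasibility study whose sample size section accepts non-significant single-predictor trends, and no stated decision turns on one diversity p-value. That limits the consequence. It does not argue for keeping noise that can be removed without new data.

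**Conclusion.** The point holds as a minor, free improvement. On the natural reading, one random draw adds avoidable noise to the retained swabs, and verdicts near the threshold can depend on it. Presence-based measures are more exposed than abundance-weighted ones. For weighted UniFrac this rests on reasoning alone.

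Pooling the set-ups, two draws disagreed in roughly 1-24% of contrasts for richness, 6-19% for presence/absence PERMANOVA at null to intermediate effects, and 0-8% for Shannon or Bray-Curtis. These figures rest on assumed read depth and community shape, 10 v 10 swabs, and unadjusted p < 0.05. The effect after false discovery rate correction is unknown. The power gain runs from nil to about 12 or 13 points and should not be promised; the secure gain is a result that no longer turns on the draw.

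The documents do not support saying that the diversity findings as a whole are unreliable. Most verdicts in set-up B did not change under any draw, and in C clear beta-diversity effects were almost unaffected.

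**What to change.** Keep the depth and the retained swabs as they are, and change only how the metrics are computed:
- use the closed-form expected richness (vegan rarefy function) in place of observed richness from a draw;
- average every other alpha metric, and each of the three dissimilarity matrices, over at least 100 draws before the rank-sum, Adonis and ordination steps;
- record the seed and the number of draws, and report how often each verdict changes across the draws.

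The cost is computing time only: no further patients, swabs or sequencing. The change does not bring back swabs lost below the depth, restore the within-patient pairing, or make up for the low depth; those need separate attention.

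### The swab comparison is defined within patient but tested unpaired; lost swabs do not justify dropping patient identity, and moderate shifts may be missed as a result

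*Combined protocol and SAP*

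**What the plan says.** All of this is in the Combined protocol and SAP.

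- **Microbiota analysis, the comparison:** "Pre-surgery data was used as a baseline, thus, each patient had their internal control", and the individual patient's "pre- and post- skin swab samples were compared".
- **Microbiota analysis, the test:** "For testing statistically significant differences between populations, the nonparametric Wilcoxon rank-sum test was used". The reason opens with "Due to the sample losses from rarefaction, the" and runs on to "unpaired test was used". The losses come from "rarefaction of samples down to an even depth of ~ 1000 sequences per sample".
- **Layout:** the data are "swabs obtained from 3 different sites", which Aim 1 lists as the stoma and the thigh skin on each side. The section does not say how sites enter a test, which contrasts are tested, how many swabs were lost, or how many complete pairs remain.
- **Sample collection:** ten collection times, beginning "Pre-op stage 1/day of the procedure, 3+/-7 days of stage 1 post-op, pre-op of stage 2/day of procedure".
- **Related methods:** FDR correction is applied, but its family is not defined. PERMANOVA (adonis) and DESeq2 are named without a permutation scheme or design formula.

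**The concern.** The question asked of the swabs is how each patient changes from that patient's own baseline. An unpaired test treats pre and post swabs as if they came from different people, so stable differences between patients stay in the error term. With only ten patients, within-patient control is a main source of precision, and the choice can leave a real, moderate change reported as not significant.

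Losing swabs is a reason not to rely on complete pairs alone. It is not a reason to treat the remaining swabs of one patient as unrelated, because methods exist that use both the paired and the lone swabs.

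**Working it through.** **Plan's own figure.** None is given for the swab comparison. The only power statement (80% for r = 0.71, n = 10, two-sided 0.05) concerns cytokines. A fixed-regressor t test on 8 df, with noncentrality √10 × 0.71/√(1 − 0.71²) = 3.19, gives 79.7%. It reproduces but has no bearing here.

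**Inputs.** From the document: 10 patients, 3 sites, 10 collection times. Assumed, because the document gives none: correlation ρ = 0.3/0.5/0.7, random loss of 0/20/30%, shift of 1 SD (others where stated), one swab per patient per visit at one site, roughly normal metric with equal spread.

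**Step 1: why complete pairs alone will not do.** The smallest two-sided signed-rank p with k pairs is 2/2^k, so 5 pairs give 2/32 = 0.0625. Pairs follow Binomial(10, (1 − loss)²). The chance of 5 or fewer is 27% at 20% loss and 65% at 30%. At 30% loss and ρ = 0.5, simulated power is 15% for signed-rank and 33% for rank-sum.

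**Step 2: loss shrinks the dependence but does not remove it.** With n₁ and n₂ swabs, of which n_c are paired, and SD 1:

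Var(difference in means) = 1/n₁ + 1/n₂ − 2ρ·n_c/(n₁n₂).

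An unpaired analysis omits the last term.

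- No loss (10, 10, 10): 0.20 − 0.20ρ. At ρ = 0.5 the assumed SE is too large by √(0.20/0.10) = 1.41.
- 20% loss, expected counts (8, 8, 6.4): 0.25 − 0.20ρ. Factor √(0.25/0.15) = 1.29.
- 30% loss (7, 7, 4.9): 0.286 − 0.20ρ. Factor √(0.286/0.186) = 1.24.

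**Step 3: type I error of the rank-sum test.** The exact level for 10 against 10 independent swabs is about 4.3%. At ρ = 0.3/0.5/0.7, simulation gives 2.1/0.9/0.2% with no loss and 2.4/1.5/0.6% at 20% loss.

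**Step 4: power for 1 SD.** The comparator is the unequal-variance partially overlapping samples t-test (POS-t), which uses every surviving swab (6,000 runs per cell at unadjusted 0.05; 1,200 runs for FDR). The FDR rows take one baseline, hence 9 contrasts, all shifted, with constant correlation.

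| Setting | Rank-sum, ρ 0.3/0.5/0.7 | POS-t |
|---|---|---|
| 0.05, no loss | 51/53/54% | 66/81/95% |
| 0.05, 20% loss | 41/40/40% | 49/58/71% |
| 0.05, 30% loss | 34/33/32% | 40/47/55% |
| FDR, no loss | 36/36/38% | 54/72/94% |
| FDR, 20% loss | 26/26/26% | 33/46/60% |
| FDR, 30% loss | 20/18/20% | 24/31/41% |

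A random-intercept mixed model gives a similar picture at 20% loss: 49/61/76% against 44/41/40% (400 runs, about ±5 points).

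**Step 5: where the gain fades.**

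- *Decaying correlation* (0.7 per visit on 70% of variance), FDR, all visits shifted 1 SD. Rank-sum against POS-t is 37 v 47% with no loss, but 26 v 27% at 20% loss and 19 v 21% at 30%. Another set of runs gave 28 v 31% and 19 v 22% with loss.
- *Decay with only the last three visits shifted:* 28 v 26%, 18 v 16% and 14 v 11% at 0/20/30% loss.
- *Low correlation at a strict step* (0.05/9 = 0.0056), 2 SD, 20% loss: 64 v 55% at ρ = 0.1 and 67 v 54% at ρ = 0, so POS-t loses.
- *Large shift* (2 SD, unadjusted 0.05, 20% loss): 95/95/96% v 96/98/99%, so either test finds it.

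**Step 6: if sites were pooled.** With three sites entered as 30 against 30 independent swabs, rank-sum type I error rises from 1.0% to 9.8% as patient-by-visit variance goes from 0 to 0.3 of the total. Another set of runs, with patient variance 0.3, went from 2.4% to 9.0%.

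**The case against.** The choice is disclosed with a reason. In the plainest layout it errs on the safe side, so it creates no false claims. This is a ten-patient feasibility study, and the Sample Size Justification accepts non-significant single comparisons if overall model fit is significant. Correlation over more than a year may well decay, and with loss the gain is then only 1 to 3 points. The alternatives have faults of their own. On an untransformed lognormal metric (log SD 0.8, 20% loss) POS-t had 31/36/47% power against 41/40/40% for rank-sum. The section is written in the past tense, so putting a newly chosen test in first place would be post hoc. The stoma may also lack a like-for-like baseline, since none exists before surgery.

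Much of this stands. It limits the size of the cost and argues for adding an analysis rather than replacing one. It does not rescue the stated reason, because lost swabs leave the dependence among surviving swabs in place (step 2). The allowance in the Sample Size Justification is illustrated with cytokine model fit. It softens the consequence but does not make an unpaired test suit a within-patient question.

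A reader might infer that the reported p-values are too small. That would need sites pooled as independent swabs, and the document does not say they were. Nor does unequal spread show it. With loss of 0% and 50% and doubled SD at the high-loss visit, rank-sum type I error is highest at zero correlation (about 7.5%), so that is an unequal-variance problem and not a pairing error.

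**Conclusion.** The mismatch holds: a within-patient comparison is tested without patient identity, for a reason that does not support it. Confidence in this is high.

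Confidence in the size of the cost is moderate, because correlation, loss and effect size are all assumed. With one swab per patient per visit at one site, equal spread and constant correlation of 0.3 to 0.7, the rank-sum test runs at about 2% down to 0.2% type I error without loss. For a 1 SD shift at unadjusted 0.05 it gives up about 15 to 41 points of power with no loss (66 − 51; 95 − 54) and 8 to 31 points at 20% loss (49 − 41; 71 − 40). A reader might infer that a patient-aware test would recover this in any case. The document gives no correlation to support that, and step 5 shows plausible settings with little gain or a loss.

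This should be fixed, but it does not by itself invalidate the reported results.

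**What to change.** - Name each pre/post contrast. Analyse one site at a time, with one value per patient per visit.
- Add a patient-aware analysis that uses every surviving swab, such as a mixed model with a patient effect, or POS-t on a metric transformed to rough symmetry. Choose the method and transformation without reference to the results.
- Report it beside the existing rank-sum result, labelled as added after that analysis.
- For the stoma, state which pre-surgery swab serves as baseline.
- Report swabs lost and complete pairs per visit and site, and define the FDR family.
- As a secondary matter, keep patient in the DESeq2 design and respect patient in the adonis permutations for pre/post contrasts, and state both.

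Cost: some re-analysis of existing data in R and revised SAP wording, with no new samples. The added analysis rests on distributional assumptions that ten patients cannot test well, and it may have lower power than rank-sum when correlation is near zero. No choice of test repairs selective loss of low-biomass swabs, which is a further reason to report losses by visit and site.

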The critical limiting factor to the prior U.S. introduction of this technology has been an up to 30% infection rate at the implant/skin interface in European patients. Evolving designs and surgical techniques have lowered this incidence, but it remains remarkable that 70% to perhaps 95% of European patients now remain infection free by simply using mild soap and shower hygiene at the stoma, and avoiding the use of antibiotics. In fact antibiotics and disinfectants have been found to be counter productive and lead to antibiotic resistance. It is increasingly evident that the key to this improbable success is the biology and presence of a mutualistic-commensal microbiota at the skin/implant interface. These “good bacteria” are the “guard dogs at the gate”.

Microbiome studies: Traditionally, wound microbiotas have been characterized by culture based assays. Cultures, however, account for only 3% of the bacterial strains actually present. A recent study, reported that, on average, culturing techniques underestimated microbial load by 2.34 logs ($P < 0.0001$), and in some cases greater than 6 logs. Bacterial cultures, because they are designed to select for specific pathogens, are unable to grow and recognize most of the other resident skin microbiota. These non-molecular techniques do not allow a full understanding of the complexity of stomal colonization in both the diseased and healthy states.

The relationships between the bacterial subsets within an ecological community are complex. There is strong evidence to suggest that microbes that are commonly thought of as pathogens can live commensally on the skin. In fact, bacteria from the genera *Staphylococcus*, *Corynebacterium*, *Propionibacterium*, *Streptococcus* and *Pseudomonas*, may directly benefit the host (mutualism) and only rarely will they become pathogens. Recent developments in molecular based technology have now paved the way to more advanced genome based techniques for identifying bacterial ecologies (microbiome). Techniques based upon distinct bacterial molecular markers, such as 16S rRNA are now being employed to truly understand the complexity and complicity of the human microbiome.

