The purpose of this study is to investigate the clinical implementation of a new percutaneous prosthetic attachment system (Safety Study of Percutaneous Osseointegrated Implants for Prosthetic Attachment; separate IRB # 00082763) by determining the resident microbial ecology of the implant exit site and to simultaneously study the systemic and local stomal immune responses. We will use two, state-of-the-art, pre- and post-surgery bacterial monitoring technologies: these procedures are intended to facilitate the early prediction, detection, and treatment of infection, as well as to provide follow-up data that can potentially be used to advantageously manipulate the stomal microbial environment in future clinical trials.

Objectives

The objective of this study is to follow 10 patients implanted with a percutaneous osseointegrated exoprosthetic docking system (PODS) for a period of one year. This PODS

technology requires invasive surgery to skeletally attach a metal implant, which protrudes from the long bone and exits the stump skin of the amputee patient (IRB# 00082763, as above). All stomas are colonized by local skin bacteria; colonization does not necessarily result in infection. Over time, the presence of this skin penetrating foreign object (implant) will cause measurable changes in the bacterial population (microbiota) at and around the PODS exit site.

It is anticipated that the evolving microbiota, in concert with measurable changes in the local and systemic cytokine responses, will reveal patterns associated with mutualistic-commensal bacteria and/or pathogenic bacteria related to the stages of chronic wound healing. These patterns could be used to determine the presence of a stable uninfected stoma or the progression of a stomal infection. Hopefully, this information will allow timely intervention to prevent infection, i.e. by detecting early stages of infection or discerning common patterns of stable mutualistic-commensal bacterial strains, effective intervention protocols (antibiotics, probiotics or manipulation of the stomal and skin microbiota) may be developed to avoid patient morbidity and assure implant survival.

The study aims will test the following:

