with the onset of inflammation and/or infection. With a sample size of 10, there is 80% power using a two-sided alpha 0.05 comparison, to detect a correlation of $r=0.71$ or greater. Converting this to a coefficient of determination, $r^2 = 0.50$, the multivariable model would have to account for 50% of the variability in pro-inflammatory cytokines concentration. Since cytokines is measurable, going up or down across healing time in an anticipated fashion, with time being one of the predictor variables making up the multivariable curvilinear correlation, it is reasonable to assume that this magnitude of correlation will be observed in this study. Furthermore, the repeated measurements increase the statistical power somewhat. The study, then, is adequately powered to demonstrate the feasibility of microbiota, and pro-inflammatory cytokines/markers as indicators of inflammation and/or infection.

Microbiota analysis

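### DESeq2 at default settings can mask a previously rare organism that takes over one or two stomas; the plan should state the contrast and group sizes and list every flagged count

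*Combined protocol and SAP*

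**What the plan says.** Under Statistical Methods, Data Analysis and Interpretation, the Microbiota analysis text specifies OTU-level differential abundance in one clause: "the DESeq2 and phyloseq packages were used with default settings". It does not give the design formula, the contrast, the number of samples per group or any treatment of extreme counts.

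The same section takes pre-surgery swabs as each patient's baseline, samples three sites, rarefies to about 1000 reads per sample, and reports that some samples were lost to rarefaction without saying how many. It also lists Wilcoxon rank-sum tests, alpha and beta diversity, PERMANOVA, Dirichlet multinomial mixtures and ordination.

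On size: "A sample size of n=10 patients will be used". On infection, the Background cites an "up to 30% infection rate at the implant/skin interface" and says that "70% to perhaps 95% of European patients now remain infection free". The Objectives hope to allow timely intervention "by detecting early stages of infection or discerning common patterns of stable mutualistic-commensal bacterial strains".

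**The concern.** A pathogen that overgrows one stoma appears in the OTU table as one very large count among small ones. An outlier rule designed for technical artefacts treats such a count as an artefact. In this study it may be the biology of interest.

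The document never mentions the rule, because it arrives with the word default. A reader of a null OTU result therefore could not tell whether no organism emerged or whether one emerged and its count was replaced. With 10 patients and the cited infection rates, one or two affected patients is a likely outcome.

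**Working it through.** **The plan's own figure.** The only power statement is 80% at two-sided alpha 0.05 for r = 0.71 with n = 10. A fixed-predictor noncentral t with 8 df and noncentrality √10 × 0.71/√(1 − 0.71²) = 3.19 gives 0.797, so it reproduces. It does not bear on this point.

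**How many infected patients.** Infection-free proportions of 70% to 95% imply 5% to 30% infected, or 0.5 to 3 of 10. The binomial probability of exactly one or two infected of 10 is 0.39, 0.58, 0.57 and 0.35 at rates of 5%, 10%, 20% and 30%.

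**The rule (assumed software behaviour).** Cook's distance is D = (R²/p) × h/(1 − h)², with R² = (y − μ)²/(μ + αμ²). The dispersion α comes from a trimmed within-group variance (trim 1/4, floor 0.04). For 10 v 10, p = 2 and h = 1/10, so D = R² × 0.1/(2 × 0.81) = 0.0617 R². The cutoff is F(0.99; 2, 18) = 6.01, so a count is flagged when R² exceeds 6.01/0.0617 = 97.4.

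**Two hand examples.** Each has one bloom to 500 of 1000 reads and true dispersion 1, taking the negative binomial variance as the trimmed estimate.

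- *Rare before, 5 reads.* Group mean (9 × 5 + 500)/10 = 54.5; overall mean (54.5 + 5)/2 = 29.75; variance 5 + 25 = 30. α = (30 − 29.75)/29.75² is below the floor, so 0.04. R² = 445.5²/(54.5 + 0.04 × 54.5²) = 1145 and D = 70.7: flagged.
- *Common before, 50 reads.* Group mean 95; overall mean 72.5; variance 50 + 2500 = 2550. α = (2550 − 72.5)/72.5² = 0.471. R² = 405²/(95 + 0.471 × 95²) = 37.7 and D = 2.33: not flagged.

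**Why the number of blooms matters.** A trim of 1/4 drops the 2 largest squared deviations in a group of 8 or 10, but only 1 in a group of 5 or 7. When a bloom survives the trimming it inflates α, and nothing is flagged.

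**Simulation.** Negative binomial counts, true dispersion 0.5 to 4 (0.5 to 3 in the 0.5% rows). Background abundance, bloom size and dispersion are all assumptions. Ranges span the dispersions and repeated runs.

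| Samples per group | OTU share, before to bloom | Blooms | Runs with at least one bloom flagged |
|---|---|---|---|
| 10 | 1% to 80% | 1 | 96–100% |
| 10 | 1% to 80% | 2 | 79–100% |
| 10 | 1% to 80% | 3 | 0% |
| 8 | 1% to 80% | 2 | 77–100% |
| 5 or 7 | every setting tried | 2 | 0% |
| 3, 5 or 7 | 0.5% to 50% | 1 | 87–100% |
| 10 | 1% to 30% | 2 | 36–80% |
| 10 | 5% to 80% | 1 | 37–77% |
| 10 | 5% to 80% | 2 | 7–21% |
| 10 | 5% to 30% | 1 | 1–10% (1–7% in one set of runs) |
| 10 | 10% to 80% | 1 | 4–14% |
| 70 (pooled visits) | 0.5% to 50% | 1 to 4 | about 100% |
| 70 (pooled visits) | 0.5% to 50% | 14 | 0% |

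With 7 bloom samples of 70, all seven are flagged in only 5% to 7% of runs, so most of the signal stays. In an infected versus uninfected contrast with one or two infected samples, that group has fewer than three replicates and is not flagged.

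**Effect on the test (10 v 10, 0.5% to 50%).**

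| Blooms | Handling off: median log2 fold change; nominal p < 0.05 | Handling on |
|---|---|---|
| 1 | 3.4–3.5; 76–100% | about 0–0.1; 7–16% |
| 2 | 4.4–4.5; 97–100% | 0.1–0.5; 20–34% |

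The Wilcoxon test does not fill the gap: at 10 v 10 it rejects in 3% to 4% of runs with one bloom and 6% to 10% with two.

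**The case against.** A reader might infer that the emerging organism is removed before testing and that the study would then report that none emerged. The documents do not support that. With 7 or more replicates the count is replaced and the OTU is still tested. With 3 to 6 the p-value is blanked after fitting. The diversity, PERMANOVA, mixture and ordination analyses are not described as using replaced counts, and the section also describes comparing each patient's own pre- and post-surgery swabs. A sample dominated by one taxon remains visible in those data. Nothing says DESeq2 is the tool meant to detect infection.

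Three further arguments carry weight.

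- The contrast is unstated. With three sites and about ten visits, groups could hold many more than 10 samples, or fewer than 8 after rarefaction losses.
- The Background says the genera of interest can live on skin as commensals. Expansion of an organism already present is therefore a central scenario, and there the default mostly keeps the count.
- The default is a legitimate guard. A group test that reaches p < 0.05 because of one patient reports an anecdote as a group difference, so simply switching the handling off is a debatable trade.

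All of this stands and limits the point. It does not remove the ambiguity of a null OTU result: the plan fixes none of the conditions that decide whether a bloom is kept, and no stated output shows what was flagged.

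**Conclusion.** The point holds in a narrow form and is minor. If the contrast is pre- versus post-surgery with about 8 to 10 samples per group, an OTU at about 1% or less that comes to dominate one stoma is nearly always flagged. With two stomas it is usually flagged (about 80% to 100% for 1% to 80%). Its signal is then largely lost from the DESeq2 test. With one bloom of a rare organism the flag is also usual in groups of 3 to 7. Outside these cases the effect is much weaker or absent.

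This rests on the default behaviour of the software, which the document does not describe; on DESeq2 receiving counts of roughly 1000 reads per sample; on the assumed abundances and dispersions; and on a re-implementation of the rule, not the package itself.

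**What to change.** Keep the default as the group-level test. In the Microbiota analysis section:

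1. State the DESeq2 design, the contrast, and the replicates per group after rarefaction losses.
2. Add as a stated output a listing of every OTU count flagged or replaced, and every OTU given a missing p-value, with patient, visit, site and clinical infection status.
3. Report a sensitivity run with replacement and filtering off (`minReplicatesForReplace = Inf`, `cooksCutoff = FALSE`), labelled descriptive and shown with per-patient counts.

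The cost is one listing and one extra run on data already in hand. The downside is that calls in the sensitivity run may rest on one or two patients, which the per-patient counts make visible. No clinical procedure changes.
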